2.1. Multiplicity Adjustment

Multiplicity adjusted analyses will be performed on the primary and key secondary objectives to control the overall family-wise Type 1 error rate at a 2-sided alpha level of 0.05 within each ISA. The graphical multiple testing procedure described in Bretz et al. (2009, 2011) will be used. This approach is a closed testing procedure; hence, it strongly controls the family-wise error rate across all hypotheses (Alosh et al. 2014).

[Figure GPIF.2.1](#) provides the details of the graphical multiple testing procedure. Because the 2 types of estimands (treatment regimen and efficacy estimands) are intended for distinct purposes, no multiplicity adjustment will be made for conducting separate analyses on the same objectives. Unless otherwise specified, there will be no multiplicity adjustments for evaluating exploratory objectives and safety assessments.

Analysis for change in PROMIS Sleep-related impairment short form 8a and PROMIS Sleep disturbance short form 8b is specified in the integrated efficacy analysis plan to be tested subject to the submission wise error rate control strategy (Bretz and Xi 2019, Vandemeulebroecke et al. 2024) by conducting a pooled analysis across the 2 ISAs.

**Figure GPIF.2.1****Graphical testing scheme for Study GPIF.**

3. Analysis Sets

Table GPIF.3.1 describes the populations that will be used for statistical analyses within each ISA of the master protocol. Additional intervention-specific populations for analyses may be described in the respective ISA.

Table GPIF.3.1. Description of Analysis Population

| Analysis Population | Description |
|---------------------------------|---|
| Entered | All participants who sign informed consent. |
| Randomized | All participants who are randomly assigned a study treatment (double-blind). |
| Modified intent-to-treat (mITT) | All randomized participants who are exposed to at least 1 dose of study intervention. |

Table GPIF.3.2. Description of Analysis Data Point Sets

| Analysis Set | Description |
|-----------------------------|---|
| Full analysis set (FAS) | Data obtained during treatment period of set of participants from the mITT population, regardless of adherence to study intervention. |
| Efficacy analysis set (EAS) | Data obtained during treatment period of set of participants from the mITT population, excluding data after discontinuation of study intervention (last dose + 7 days) and for ISA1, excluding data after initiating PAP therapy. |
| Safety analysis set (SS) | Data obtained during treatment and safety follow-up period of set of participants from the mITT population, regardless of adherence to study intervention. |

Abbreviations: EAS = efficacy analysis set; FAS = full analysis set; ISA = intervention-specific appendix; mITT = modified intent-to-treat; PAP = positive airway pressure; SS = safety analysis set.

4. Statistical Analyses

4.1. General Considerations

Statistical analysis will be the responsibility of Eli Lilly and Company (Lilly) or its designee. Statistical analysis for each ISA will be conducted individually and a combined analysis with both ISAs is not planned. All analyses specified will apply to both ISAs unless the analysis is specified as ISA-specific.

The SAP will be finalized prior to the unblinding of the first ISA.

Some analyses and summaries described in this analysis plan may not be conducted if not warranted by data (for example, too few events to justify conducting an analysis). Additional exploratory analyses of the data will be conducted as deemed appropriate.

Efficacy analyses will be conducted on all participants randomly assigned to study intervention according to the treatment to which the participants are assigned and were exposed to at least 1 dose. For the “treatment regimen” estimand, the analysis will be conducted using the FAS. To minimize missing data, participants randomly assigned to study intervention who prematurely discontinue study treatment will be encouraged to remain in the study. However, some participants may choose to permanently discontinue from the study which will lead to missing endpoints. Details on handling missing values can be found in Section 4.1.2. For the “efficacy” estimand, the analysis will be conducted using the EAS.

Safety analysis will be conducted using the Safety Analysis Set. Selected safety analyses may be conducted after excluding the data after permanent discontinuation of the study intervention. For the safety related parameters, the definition of baseline and postbaseline are specified in Table GPIF.4.1.

Table GPIF.4.1. Baseline and Postbaseline Definition for Safety Analyses

| Analysis Set | Analysis Type | Baseline | Postbaseline |
|--------------|--|---|--|
| SS | 1.1) Treatment-Emergent Adverse Events | The baseline period is defined as the start of screening and ends prior to the first dose of study treatment (typically at Week 0). If the first dose date is missing, then the randomization date will be used instead of first dose date. | Starts at or after the first dose of study treatment and ends at the end of the study period (including off-drug follow up visit). |
| SS | 1.2) Treatment-Emergent Abnormal Laboratory Results ^a and Vital Signs | For laboratory results, baseline period is defined as prior to the first dose time and will include all scheduled and unscheduled measurements. If the first dose time is missing, then any data collected on the date of the first dose will be treated as baseline. For vital signs, baseline period is defined as measurements collected prior to the first dose. | Postbaseline will be defined as after the baseline period through the end of the study participation. All scheduled and unscheduled measurements will be included. |

| Analysis Set | Analysis Type | Baseline | Postbaseline |
|--------------|---|---|---|
| | | If the first dose date is missing, then the randomization date will be used instead of first dose date. | |
| SS | 1.3) Change from Baseline for Laboratory Results ^a , and Vital Signs | The last scheduled and unscheduled nonmissing assessment recorded during the baseline period defined above (1.2). | Postbaseline will be defined as above (1.2). Only scheduled visits will be included. The ED visits are considered scheduled visits. |

Abbreviations: ED = early discontinuation; SS = Safety Analysis Set.

^a Immunogenicity related analysis is specified in Section [4.6.3.5](#).

For AHI analyses, baseline is defined as the last nonmissing measurement prior to the first dose.

The following paragraphs define selection of the PRO response which will be used for analysis at baseline and postbaseline visits. To select the baseline observation for PROs which are planned to be completed on the same day as the PSG (ESS, FOSQ, PROMIS, PGIS, SF-36v2 acute form, and EQ-5D-5L), the observation completed on the day or on the next day of the start of the baseline PSG will be selected. If multiple responses are completed within this period, the last response given within this timeframe will be selected. If no response was provided within this timeframe, the latest observation completed prior to the first dose will be selected. If a baseline still cannot be identified, the earliest observation within a 7-day window from the start of treatment date will be selected.

For postbaseline visits with a planned PSG measurement, the response for the PROs which are planned to be completed on the same day as the PSG (ESS, FOSQ, PROMIS, PGIS, PGIC, SF-36v2 acute form, and EQ-5D-5L) will be selected in the following way. If available, the observation completed on the day or on the next day of the start of the PSG will be selected. If multiple responses are completed within this period, then the last response given within this timeframe will be selected. If no response was provided in this timeframe, the latest observation completed within the visit window will be selected. If a measurement for the visit still cannot be identified, then the observation within a 7-day window around the start of visit date that is closest to the visit start date will be selected.

For postbaseline visits without a planned PSG measurement, the response for the PROs (ESS, FOSQ, PROMIS, PGIS, PGIC, SF-36v2 acute form, and EQ-5D-5L) will be identified by selecting the latest observation completed within the visit window. If a measurement for the visit cannot be identified in this manner, then the observation within a 7-day window around the start of the visit date that is closest to the visit start date will be selected.

To select the baseline observation for the PHQ-9 and C-SSRS, if multiple responses are completed prior to the first dose and there are no differences in these responses, the observation completed most recently, prior to the first dose, will be selected. If multiple responses are completed prior to the first dose and there are differences in these responses, the approach differs based on the questionnaire. For the PHQ-9, the response with the worst total score will be

selected; for the C-SSRS, the worst response for each question will be selected and each of the worst responses will be combined into a single response which will be used for analysis. For each postbaseline visit, the same approach to select a response in the case of multiple responses within the same visit window will be carried out.

For all other analyses, baseline is defined as the last nonmissing measurement prior to the first dose unless otherwise specified.

For AHI, if there are multiple observations for the same visit, then the later observation will be selected.

Statistical treatment comparisons will be performed between tirzepatide MTD and placebo. Unless otherwise noted, all tests of treatment effects will be conducted at a 2-sided alpha level of 0.05, and the confidence interval will be calculated at a 2-sided 95% level. In statistical summaries and analyses, participants will be analyzed as randomized. Analysis models will use geographic region (US/OUS) as a covariate when applicable.

Analysis of covariance will be used to analyze continuous variables collected only at baseline and endpoint. Unless otherwise specified, the model will include treatment and strata (geographic region [US/OUS], AHI stratum [not severe (AHI <30), severe (AHI \geq 30)], and gender) as fixed effects and baseline as a covariate.

MMRMs will be used to analyze continuous variables collected at baseline and more than 1 postbaseline visit. For the MMRM analysis, REML will be used to obtain model parameter estimates for continuous longitudinal variables. All the longitudinal observations at each scheduled postbaseline visit will be included in the analysis. The model will include the fixed class effects of treatment, strata (geographic region [US/OUS] and gender), visit, and treatment-by-visit interaction, as well as the continuous, fixed covariate of baseline value. For analyses of variables other than AHI, the AHI stratum will also be included in the model. Significance tests will be based on least squares means and Type III tests.

For continuous measures, summary statistics may include sample size, mean, standard deviation, median, minimum, and maximum for both the actual and the change from baseline measurements. Least-square means and standard errors derived from the analysis models will also be displayed for the change from baseline measurements. Treatment comparisons will be displayed showing the treatment difference least-square means and the 95% confidence intervals for the treatment differences, along with the p-values for the treatment comparisons.

For categorical measures, summary statistics may include sample size, frequency, and percentages. Fisher's exact test or Pearson's chi-square test will be used for treatment comparisons unless otherwise specified.

Not all analyses described in this SAP will necessarily be included in the CSRs. Any analysis described in this SAP and not provided in the CSR would be available upon request.

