Fasting Visit		X	X	X	X	X	X	X	X	X	X	X	X	See footnote b.	
Physical Evaluation															
Height	X														
Weight	X	X	X	X	X	X	X	X	X	X	X	X	X	Weight measurements should be obtained per the instructions in Section 10.8.	
Waist circumference		X					X			X	X	X		Waist circumference should be obtained per the instructions in Section 10.8.	
Hip circumference		X					X			X	X	X		Hip circumference should be obtained per the instructions in Section 10.8.	
Neck circumference		X					X			X	X	X		Neck circumference should be obtained per the instructions in Section 10.8.	
Vital signs	X	X	X	X	X	X	X	X	X	X	X	X	X	Includes PR and BP. Measured after participant has been sitting at least 5 minutes. Vital-sign measurements should be taken before obtaining an ECG tracing and before collection of blood samples for laboratory testing. See Sections 8.2.2 and 10.8.	
Complete physical examination	X													The complete physical examination is performed (excludes pelvic, rectal, and breast examinations unless clinically indicated).	
Symptom-directed physical assessment		X (refer to Comment)												Symptom-directed physical assessment from V2 through V11 and ED will be conducted at the discretion of the PI, as indicated based on participant status and standard of care.	

	Study Period I - Screening	Study Period II - Treatment												Study Period III - Post-Treatment Follow-up	Comments
		2	3	4	5	6	7	8	9	10	11	ED			
Visit number	1												801		
Weeks from randomization	-4	0	4	8	12	16	20	24	36	48	52	-	See footnote a		
Visit interval tolerance (days)	-14 to +21	-	±3	±3	±3	±3	±7	±3	±7	±3	±7	±7	±3		
Fasting Visit		X	X	X	X	X	X	X	X	X	X	X		See footnote b.	
															May be performed by qualified personnel per local regulations.
12-lead ECG (local)	X											X	X		ECG measurements should be obtained per the instructions in Section 8.2.3.
Wearable Devices and PSG Assessments															
Schedule Sleep Center Study for PSG	X					X				X					PSG results must be reviewed to confirm eligibility prior to randomization.
Sleep Center Study for PSG	X					X				X					PSG at V7 and 11 may be scheduled for any day +/- 14 days.
Participant wears the WatchPat300	X		X	X	X	X				X					Applicable only to participants in GPII (off PAP). Training documents will detail information on the dispensation, wearing, and return process.

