Baseline is defined as the last non missing measurement at or before the randomization visit (Visit 2) unless otherwise specified.

Analysis of covariance will be used to analyze continuous variables collected only at baseline and endpoint. The model will include treatment and strata (pooled country/geographic region, AHI stratum [moderate (AHI  $\geq 15$  and AHI  $< 30$ ), severe (AHI  $\geq 30$ )] and gender) as fixed effects and baseline as a covariate. The ANCOVA model for AHI analysis will include baseline AHI instead of the AHI stratum as a fixed covariate.

The MMRM analysis, a restricted-maximum-likelihood-based model, will be used to analyze continuous longitudinal variables. All the longitudinal observations at each scheduled postbaseline visit will be included in the analysis. The model will include the fixed class effects of treatment, strata (pooled country/geographic region and gender), visit, and treatment-by-visit interaction, as well as the continuous, fixed covariate of baseline value. For analyses of variables other than AHI, the AHI stratum will also be included in the model. Significance tests will be based on least-squares means and Type III tests.

For continuous measures, summary statistics may include sample size, mean, standard deviation, median, minimum, and maximum for both the actual and the change from baseline measurements. Least-square means and standard errors derived from the analysis models will also be displayed for the change from baseline measurements. Treatment comparisons will be displayed showing the treatment difference least-square means and the 95% confidence intervals for the treatment differences, along with the p-values for the treatment comparisons.

For categorical measures, summary statistics may include sample size, frequency, and percentages. Fisher's exact test or Pearson's chi-square test will be used for treatment comparisons unless otherwise specified.

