4.4. Secondary Endpoints Analysis

4.4.1. Key Secondary Endpoints

A graphical approach for multiple comparisons will be used to strongly control the overall Type 1 error (2-sided alpha level of 0.05) for testing the superior treatment effect of tirzepatide MTD over placebo including the key secondary endpoints as listed below.

- percent change in AHI at Week 52
- percent of participants with $\geq 50\%$ AHI reduction at Week 52
- percent of participants at Week 52 with
 - AHI <5 or
 - (AHI 5 through 14 and ESS ≤ 10)
- percent change from baseline to Week 52 in body weight
- change from baseline to Week 48 in SBP
- change from baseline to Week 52 in C-reactive protein (high-sensitivity C-reactive protein)
- change in sleep apnea-specific hypoxic burden (% minutes/hour)
- change in PROMIS Sleep-related impairment short form 8a, and
- change in PROMIS Sleep disturbance short form 8b.

Analytical approaches for the hierarchical assessment of PROs are described in Section 4.4.3.1 and a summary of the analysis approach for all other key secondary endpoints is provided in Section 4.4.1.1.

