4.4.1.1. Main Analytical Approaches

Analysis of percent change in AHI, percent change from baseline to Week 52 in body weight, change from baseline to Week 52 in log of high-sensitivity C-reactive protein, change from baseline to Week 48 in SBP, change from baseline to Week 52 in PROMIS Sleep-related impairment, change from baseline to Week 52 in PROMIS Sleep disturbance, and change from baseline to Week 52 in log of hypoxic burden will be conducted in a manner similar to the primary efficacy analyses using an ANCOVA model with treatment, strata (geographic region [US/OUS], AHI stratum [not severe (AHI <30), severe (AHI \geq 30)], and gender), and baseline of the corresponding variable as a covariate for the treatment regimen estimand. If the hypoxic burden is reported to be 0, log (1) will be used in place of the log of hypoxic burden. The analysis method utilizing data from both ISAs for change from baseline to Week 52 in PROMIS sleep Impairment and PROMIS Sleep disturbance is described in the integrated efficacy analysis plan.

For the efficacy estimand, the MMRM analyses will be conducted as described in Section 4.1. For both estimands, analysis of percent change in AHI will adjust for the continuous, fixed baseline value of AHI instead of the baseline AHI stratum (not severe, severe).

Comparisons at the 52-week visit between the treatments relative to the proportion of participants achieving \geq 50% AHI reduction and AHI <5 or (AHI 5 through 14 and ESS \leq 10) will be conducted using logistic regression analysis including the following terms as a covariate:

- treatment
- geographic region (US/OUS)
- baseline AHI, and
- gender.

Unconditional risk differences will also be provided for these endpoints using logistic regression (Ye et al. 2023).

Analysis aligned to each estimand will be evaluated at the full significance level of 0.05 contingent on reaching statistical significance of the primary objective.

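### Adding Visit 1 blood pressure as a second covariate in the SBP and DBP efficacy models would be a nearly free precision gain of unknown size; the single Visit 2 baseline is not an error

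*SAP*

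**What the plan says.** SAP 4.4.1 lists "change from baseline to Week 48 in SBP" among the key secondary endpoints, and SAP 2.1 undertakes to "control the overall family-wise Type 1 error rate at a 2-sided alpha level of 0.05 within each ISA". Change in DBP at Week 48 is an other secondary endpoint, outside that control (SAP Table GPIF.4.3).

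For the treatment regimen estimand, SBP is analysed by ANCOVA with treatment, region, AHI stratum, gender "and baseline of the corresponding variable as a covariate for the treatment regimen estimand" (SAP 4.4.1.1). For the efficacy estimand, SBP is analysed by MMRM with the class effects "as well as the continuous, fixed covariate of baseline value" (SAP 4.1). DBP uses the same MMRM. Each model therefore has one baseline BP term.

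That term follows the SAP 4.1 default: "For all other analyses, baseline is defined as the last nonmissing measurement prior to the first dose unless otherwise specified". Protocol 9.3.1 is to the same effect: "Baseline is defined as the last non missing measurement at or before the randomization visit (Visit 2) unless otherwise specified".

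In the Schedule of Activities (Protocol 1.3) the vital signs row is marked at Visit 1, Visit 2 and every later visit, with the comment "Includes PR and BP. Measured after participant has been sitting at least 5 minutes". The first dose is to be given at the end of Visit 2, after the other procedures. Protocol 10.8.5 requires three readings per parameter and makes no exception for Visit 1. Exclusion criterion 29 is judged on Visit 1 BP. SAP 4.6.4, a safety section, averages replicate readings within a visit.

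**The concern.** SBP varies from day to day, so the mean from one visit is a noisy measure of a participant's usual level. A second pre-randomization set, taken by the same procedure, should exist for practically every randomized participant, yet it does not enter the SBP or DBP efficacy model. If it carries information about Week 48 beyond what Visit 2 carries, leaving it out makes the confidence interval wider and the power lower than the collected data allow. The sample size sections give power for percent change in AHI and for a hierarchical PRO endpoint but none for SBP, so the margin for SBP is unknown.

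**Working it through.** **The plan's own figure.** The documents give no SD, effect, power or visit-to-visit correlation for SBP. The nearest figure is at least 90% power for percent change in AHI (difference 50, SD 50, 103 per arm, 25% dropout). With 103 × 0.75 ≈ 77 evaluable per arm, power is above 99.9%. The statement holds as a floor, but it says nothing about SBP.

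**Formulas.** Let r2 and r1 be the correlations of Visit 2 and Visit 1 SBP with Week 48 SBP, and r12 the correlation between the two visits. Take the Week 48 variance as 1.

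- Visit 2 only: residual variance = 1 − r2².
- Visit 1 and Visit 2: residual variance = 1 − (r1² + r2² − 2·r1·r2·r12)/(1 − r12²).
- If r1 = r2 = r, the second becomes 1 − 2r²/(1 + r12).

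These are ANCOVA formulas for complete data, ignoring the other model terms. Change from Visit 2 and the raw Week 48 value give the same contrast once Visit 2 is a covariate. All correlations below are assumed.

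**Case A: both visits predict Week 48 equally well.**

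| r | r12 | Visit 2 only | both visits | variance change | SE change |
|---|---|---|---|---|---|
| 0.4 | 0.6 | 0.840 | 0.800 | −4.8% | −2.4% |
| 0.5 | 0.6 | 0.750 | 0.688 | −8.3% | −4.3% |
| 0.6 | 0.6 | 0.640 | 0.550 | −14.1% | −7.3% |
| 0.4 | 0.7 | 0.840 | 0.812 | −3.4% | −1.7% |
| 0.5 | 0.7 | 0.750 | 0.706 | −5.9% | −3.0% |
| 0.6 | 0.7 | 0.640 | 0.576 | −9.9% | −5.1% |

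As equivalent sample size, the extremes are 0.840/0.812 − 1 = 3.5% and 0.640/0.550 − 1 = 16.4%. On the 206 × 0.75 ≈ 154 evaluable in an ISA, that is about 5 to 25 participants.

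**Case B: Visit 1 predicts less well than Visit 2.**

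| r2 | r1 | r12 | variance ratio | SE change |
|---|---|---|---|---|
| 0.6 | 0.55 | 0.65 | 0.931 | −3.5% |
| 0.5 | 0.45 | 0.6 | 0.953 | −2.4% |
| 0.6 | 0.5 | 0.7 | 0.980 | −1.0% |
| 0.6 | 0.42 | 0.7 | 1.000 | 0 |

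The gain vanishes when r1 = r2 × r12 (here 0.6 × 0.7 = 0.42), that is, when Visit 1 adds nothing once Visit 2 is known.

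**In mmHg, for the most favourable cell** (r = r12 = 0.6, assumed SD 14 mmHg, 77 per arm): SE = 14 × √0.64 × √(2/77) = 1.81 now and 14 × √0.55 × √(2/77) = 1.67 with both visits. The 95% half-width goes from 3.54 to 3.28 mmHg. An effect with 80% power now would have 85.6%.

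**Simulation check.** ANCOVA was simulated with 77 per arm, 4,000 replicates per setting, equal correlations and a true effect of −5 mmHg. Variance ratios were 0.89, 0.87 to 0.88 and 0.84 to 0.85 at r = 0.5, 0.6 and 0.7, against 0.889, 0.859 and 0.830 by formula. Mean estimates were −4.94 to −5.07 under both models, so there was no sign of bias. Restricting Visit 1 SBP to below 160 mmHg, as exclusion 29 does, made no material difference.

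**Why not average the two visits?** Averaging fixes equal weights.

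- With (r2, r1, r12) = (0.6, 0.42, 0.7), the average correlates (0.6 + 0.42)/√(2 × 1.7) = 0.55 with Week 48. Residual variance is 1 − 0.306 = 0.694, worse than 0.640 with Visit 2 alone.
- If change is still taken from Visit 2 and only the covariate is averaged, precision falls even with equal correlations. At r = r12 = 0.6, Var(Week 48 − Visit 2) = 0.8, its covariance with the average is −0.2, and the average has variance 0.8. Residual variance is 0.8 − 0.04/0.8 = 0.75, against 0.640.

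**The case against.** The strongest case on the other side is that nothing here is wrong. The baseline rule is clear and consistent across both documents, and one baseline covariate is a conventional choice. A reader might infer a bias or a Type 1 error problem; the documents support neither, and the point is about precision only. That stands.

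A reader might also infer that Visit 1 BP is discarded. It is not. It decides eligibility under exclusion 29, serves as baseline if the Visit 2 value is missing, and feeds the baseline-period minimum and maximum in the treatment-emergent vital sign analysis (SAP Table GPIF.4.1 and 4.6.4). It is absent only as an efficacy covariate.

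The documents also give reasons to doubt that Visit 1 predicts as well as Visit 2. It is nominally four weeks earlier. The fasting row is blank at Visit 1, although a footnote to the schedule is worded more broadly. The screening polysomnography belongs to Visit 1, SAP 4.3.3 shows that ISA2 participants withdraw PAP before the baseline study, and the protocol itself worries that PAP suspension may confound BP. Because both readings precede randomization, none of this biases the comparison, but it may make Case B the relevant one. The three readings per visit also already remove some of the noise.

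The added covariate touches the treatment regimen imputation as well (SAP 4.1.2), where retrieved dropouts may be few. This is a minor difficulty: Visit 1 BP should be nearly complete, and the table there already treats missing baseline data as missing at random.

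Body weight is also measured at both visits and could prompt the same suggestion. That does not weaken the point for BP.

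**Conclusion.** The point holds as an optional, nearly free improvement. The documentary facts are firm: a second triplicate pre-randomization BP is scheduled for everyone, and the SBP and DBP efficacy models adjust for one baseline value only, normally Visit 2.

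The size is not firm. It rests entirely on assumed correlations: a standard error about 2 to 7% smaller if the two visits predict Week 48 equally well, and about 0 to 3.5% smaller if Visit 1 predicts less well. The 3% variance reduction at the low end of Case A is not a guaranteed minimum, because the gain may be nil. In expectation the only loss is about one degree of freedom. The treatment contrast in these linear models estimates the same quantity with or without the extra covariate.

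A reader might conclude that SBP is underpowered or that a conclusion on it is at risk. The documents state no SBP effect, SD or power, so they cannot support that.

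**What to change.** In SAP 4.1 and 4.4.1.1, before unblinding:

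- Keep change in SBP and DBP computed from Visit 2, and keep the Visit 2 value as a covariate.
- Add the Visit 1 within-visit mean SBP as a second continuous covariate in the SBP ANCOVA and MMRM, and the Visit 1 mean DBP in the DBP MMRM. Do not replace baseline by the Visit 1/Visit 2 average.
- Use the same covariate in the SBP imputation model where the number of retrieved dropouts allows, and treat any missing Visit 1 value under the existing missing-at-random rule for missing baseline data.
- State that the within-visit averaging in 4.6.4 applies to efficacy BP.

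The cost is a few sentences and about one degree of freedom, with no new data. The SAP default leaves room for a variable-specific baseline rule, and Protocol 9.3.1 allows changes that do not alter a principal feature to be made in the SAP. Timing matters: if the covariate were added after unblinding, it would look like model selection.
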